9.7 Termination of the Study

If, in the opinion of the Investigator, the clinical observations in the study suggest that it may be unwise to continue, the Investigator may terminate the study after consultation with the Sponsor. A written statement fully documenting the reasons for such a termination will be provided to the Sponsor. In addition, the Sponsor may terminate the study at any time. Furthermore, if it becomes apparent that subject enrollment is unsatisfactory with respect to quality or quantity or that data recording is inaccurate or incomplete on a chronic basis, the Sponsor has the right to terminate the study and remove all study materials from the investigational site. A written statement will be provided to the Investigator, the Institutional Review Board (IRB) / Independent Ethics Committee (IEC), and regulatory authorities, if required. In the event a serious adverse event (SAE) is part of the reason for early termination of the study, all documentation relating to the event(s) must be obtained and filed appropriately.

10 ASSESSMENT OF SAFETY

10.1 Adverse Event Definition

An Adverse Event (AE) is defined as any untoward medical occurrence in a clinical investigation subject reported on or after the first screening date. A Treatment Emergent Adverse Event (TEAE) is any untoward medical occurrence in a clinical investigation subject or subject administered a pharmaceutical product on or after the initial administration of investigational product. An AE can therefore be any unfavorable and unintended sign (including an abnormal laboratory finding), symptom whether or not related to the medicinal (investigational) product, or disease temporally associated with the use of a medicinal (investigational) product.

The AE may be any of the following:

- A new illness
- Worsening of a pre-existing condition
- Worsening of a sign or symptom of the condition under treatment or of a concomitant illness
- An effect of the investigational product, including comparator
- A combination of 2 or more of these factors

No causal relationship with the investigational product or with the clinical study itself is implied by the use of the term "AE."

Surgical procedures themselves are not AEs, they are therapeutic measures for conditions that require surgery. The condition for which the surgery is required may be an AE. Planned surgical measures permitted by the clinical study protocol and the condition(s) leading to these measures are not AEs.

AEs fall into the categories "non-serious" and "serious."

10.2 Reporting of Adverse Events

AEs will be recorded starting with the signing of the informed consent. All AEs will be collected through the follow-up visit of Treatment Period 2. AEs that have not been directly reported to the Investigator will be promptly conveyed to the Investigator by the study staff. Investigators will additionally review any AE source documents and the subject's medical records, on a regular basis during the course of the study.

Beginning at the screening visit, and continuing for the duration of the study, subjects must be instructed to record any new AEs on the study specific symptom log. Subjects should bring the log to every clinic visit; where it will be retrieved for review by study staff prior to re-dispensing it (or issuing a new log) to the subject.

Any AE still unresolved at the Treatment Period 2 Follow-up Visit 10 (Day 36) or at the Premature Discontinuation Visit will be followed by the Investigator for at least 30 days from the last dose of investigational product. All unresolved AEs that were reported by the Investigator to be

probably drug related should be followed until the events are resolved/stabilized, the subject is lost to follow-up, or the AE is deemed irreversible.

Serious AEs must be submitted to the Sponsor within 24 hours of their discovery, even if the full information about the event is not yet available. These events should also be reported to the Institutional Review Board/Independent Ethics Committee (IRB/IEC) as needed based on local requirements.

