Subjects will return for Follow-up Visit 10 (Day 36) 14 days (+/- 2 days) after the last day of dosing in Treatment Period 2. Subjects will undergo the following assessments:

- Brief physical examination
- ECG (triplicate)
- Measurement of vital signs (blood pressure, heart rate, and respiratory rate), body temperature, and pulse oximetry

- Urine pregnancy test (females of childbearing potential)
- Collect investigational product blister card and assess investigational product accountability/compliance.
- Retrieve e-diary
- Retrieve and review Subject Medication and Symptom Log
- Record and assess adverse events, concomitant medications, and therapies (including restricted and prohibited medications)

6.3.3 **Premature Discontinuation Visit**

Subjects who complete investigational product treatment through the full study treatment course are considered to have completed treatment (even if some doses have been missed). Subjects who discontinue investigational product prior to Treatment Period 2 (Visit 10) will be considered to have prematurely discontinued and will be asked to complete the following visits (unless consent is withdrawn):

- If the decision to discontinue treatment is made during an onsite study visit (scheduled or unscheduled), perform the procedures and assessments outlined in the Premature Discontinuation Visit, regardless of where they are in the study visit schedule.
- If the decision to discontinue treatment is made while the subject is not at a study visit, schedule a visit as soon as possible, but no later than 2 weeks later, to perform the procedures and assessments described in the Premature Discontinuation Visit. Upon notification that the subject has permanently stopped dosing, the site should instruct the subject to begin entering their SOWS data daily via the e-diary.
- The subject should be scheduled to return to the clinic 2 weeks after completion of the Premature Discontinuation Visit for procedures and assessments outlined in the Follow-up Visit (Visit 6 if in Treatment Period 1 and Visit 10 if in Treatment Period 2).

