10.2.2 Relationship to Investigational Product

Association or relatedness to the investigational product will be graded as either "definitely related", "probably related", "possibly related", "unlikely related", or "not related". Determination of relatedness includes:

DEFINITELY RELATED – The adverse event:

- Follows a reasonable temporal sequence from administration of the study intervention
- Follows a known or expected response pattern to the suspected intervention, that is confirmed by improvement on stopping
- Reappearance of the event on repeated exposure that could not be reasonably explained by the known characteristics of the subject's clinical state

PROBABLY RELATED – The adverse event:

• Follows a reasonable temporal sequence from investigational product administration

- Abates upon discontinuation of the investigational product
- Cannot be reasonably explained by the known characteristics of the subject's clinical state.

POSSIBLY RELATED – The adverse event:

- Follows a reasonable temporal sequence from investigational product administration
- Could have been produced by the subject's clinical state or by other modes of therapy administered to the subject

UNLIKELY RELATED – The adverse event:

- Does not follow a reasonable temporal sequence from investigational product administration
- Is readily explained by the subject's clinical state or by other modes of therapy administered to the subject

NOT RELATED – The adverse event:

- Clearly not related to the investigational product and another cause of the event is most plausible
- A clinically plausible temporal sequence is inconsistent with the onset of the event
- Study intervention and/or causal relationship is considered biologically implausible

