4.12.1.5 Relationship to Investigational Product

Association or relatedness to the investigational product will be graded as either "definitely related", "probably related", "possibly related", "unlikely related", or "not related".

AEs with causal relationship to IMP "definitely related", "probably related", "possibly related" will be considered as 'Related' AEs; AEs with causal relationship to IMP "unlikely related", or "not related" will be considered as 'Not Related' AEs

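### Protocol 10.2 requires follow-up to resolution only for unresolved AEs rated 'probably' related, which does not fit the five-level causality scale and leaves out 'definitely related'

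*Protocol*

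**What the plan says.** Protocol 10.2 covers any AE that is unresolved at Visit 10 or at the Premature Discontinuation Visit. The general duty is that it "will be followed by the Investigator for at least 30 days from the last dose of investigational product". A second sentence sets a longer duty for unresolved AEs that the investigator reported as "probably drug related should be followed until the events are resolved/stabilized, the subject is lost to follow-up, or the AE is deemed irreversible". No other rating is named.

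Protocol 10.2.2 uses five ratings: definitely, probably, possibly, unlikely and not related. The criteria listed for *probably* include "Abates upon discontinuation of the investigational product". Those for *definitely* include a known or expected response pattern "that is confirmed by improvement on stopping", and also reappearance on repeated exposure. *Possibly* lists nothing about stopping. Besides a reasonable time sequence, its criterion is "Could have been produced by the subject's clinical state or by other modes of therapy administered to the subject".

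The two documents group these ratings differently for analysis. In SAP 4.12.1.5, definitely, probably and possibly "will be considered as 'Related' AEs". Protocol 11.8.1 counts probably and possibly as related and unlikely as unrelated, and places neither *definitely* nor *not related*.

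**The concern.** A follow-up rule keyed to causality would be expected to be at least as demanding for a stronger rating as for a weaker one. Here the rule names the second of five levels and is silent on the first. Taken at its word, a site could close an unresolved event that it rated definitely related at day 30, yet would have to keep following one that it rated probably related.

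The rating criteria add a second, weaker effect. Lessening or improvement on stopping is listed for the two higher ratings and not for *possibly*. An event that shows no such change after the drug is stopped has less support for the higher ratings, and is more likely to be placed where only the 30-day minimum applies.

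At stake is the final outcome of some drug-related events. Safety and tolerability is a primary objective (Protocol 5.1). Section 6.6 acknowledges potential physical dependence, Section 10.2.3 lists dependence and withdrawal among the events of special interest, and daily withdrawal-scale collection ends 14 days after last dose (8.4.10). A related event could remain in the AE listing as unresolved, with nothing in the protocol requiring anyone to find out how it ended.

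**Working it through.** This is mainly a textual check. The plan states no figure to reproduce.

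**1. Each rating against each rule**

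| Rating (Protocol 10.2.2) | Criterion on stopping | SAP 4.12.1.5 | Protocol 11.8.1 | Required follow-up (Protocol 10.2) |
|---|---|---|---|---|
| Definitely | Improvement listed; reappearance on repeated exposure also listed | Related | Not placed | At least 30 days |
| Probably | Abating listed | Related | Related | Until resolved or stabilised, lost to follow-up, or irreversible |
| Possibly | None | Related | Related | At least 30 days |
| Unlikely | None | Not related | Unrelated | At least 30 days |
| Not related | None | Not related | Not placed | At least 30 days |

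Of the three ratings that the SAP treats as Related, one has the longer duty and two do not.

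**2. Whether another section closes the gap**

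- Protocol 6.3.4 allows unscheduled visits for unresolved events, at the investigator's judgment. It imposes no duty.
- Protocol 10.4 concerns deaths up to 60 days after last dose.
- Protocol 10.6 concerns pregnancy outcome.
- Protocol 10.8 sets time frames for reporting SAE information, with no duration of follow-up.
- The SAP sets no follow-up duration.

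None of these requires follow-up to resolution for an event rated definitely or possibly related.

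**3. What the minimum adds after the last visit**

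Visit 10 falls "14 days (+/- 2 days) after the last day of dosing in Treatment Period 2", that is, 12 to 16 days after the last dose. Required days beyond Visit 10 = 30 − visit day:

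- visit at day 14: 30 − 14 = 16 days
- visit at day 16: 30 − 16 = 14 days
- visit at day 12: 30 − 12 = 18 days

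**4. To whom this applies**

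The 30 days run from the last dose of investigational product, which includes placebo. A subject completing Arm 1 takes the last nalbuphine dose on Period 1 Day 22. Visit 6, which is normally also Period 2 Day −1, comes about 14 days later. Period 2 Day 22 comes 22 days after that, because Day 1 directly follows Day −1. The last placebo dose is thus about 14 + 22 = 36 days after the last nalbuphine dose, and the minimum reaches about 36 + 30 = 66 days after it. The 30-day figure is the real interval from last active dose for subjects completing Arm 2 and for anyone who stops early while on nalbuphine.

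**5. How the criteria and the rule interact**

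- An event that lessens on stopping but is still present meets the abating criterion, can be rated *probably*, and gets the longer duty.
- An event that does not lessen lacks a listed criterion for both *probably* and *definitely*. It is then more likely to be rated *possibly*, with the 30-day minimum.

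**The case against.** The strongest reply is that the mismatch is narrow and mostly a drafting matter. Much of this stands.

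- **Thirty days is a floor.** A reader might infer that follow-up ends at day 30. The text says at least 30 days, and Protocol 6.3.4 provides for unscheduled visits. The gap is in what is required, not in what is allowed.
- **The rule does not defeat itself.** A reader might infer that no persistent event could ever reach the longer duty. The documents do not support that. Abating is not resolving. Section 10.2.2 sets no deadline for abating, does not say that every listed criterion must be met, and requires no downgrade if an event persists. A strict all-criteria reading would also leave a non-abating event with no alternative explanation outside *possibly*, and so in no category. Only a tendency towards *possibly* can be claimed.
- **The gap for *definitely* will seldom arise.** That rating also lists reappearance on repeated exposure, and each subject has one active period.
- **Late discontinuation is not a worse case.** A reader might infer that a late Premature Discontinuation Visit leaves a subject almost unfollowed. Such a subject is seen at that visit and again two weeks later, and the required minimum is unchanged.
- **No deliberate choice is shown.** Section 10.2 may have meant at least probably related, and the omissions in 11.8.1 suggest text carried over from a shorter scale. That is an inference. Even if correct, the text does not say so, and that reading still leaves out *possibly*.
- **Planned outputs change little.** AE outcome is a listing field in SAP 4.12.1.8. Apart from death, no planned summary reports resolution. The SAP's Related set is a tabulation rule and does not by itself imply a follow-up duration.

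These points limit the size of the problem. They do not supply a rule for *definitely* or settle the one for *possibly*.

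**Conclusion.** The point holds as a mismatch between a stated rule and the protocol's own scale. As written, *definitely related* has a weaker follow-up duty than *probably related*, *possibly related* has only the 30-day minimum, and no other section fills the gap. Two of the SAP's three Related ratings are affected. In practice the weight falls on *possibly*, which is where an event that does not abate on stopping is more likely to be placed.

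The consequence is modest. Some related events may lack a documented final outcome, mainly in Arm 2 completers and in subjects who stop early on nalbuphine. How many cannot be estimated from the documents. No efficacy result is affected. The conclusion rests on a literal reading of *probably drug related*. If at least probably was meant, the gap for *definitely* closes and the one for *possibly* remains.

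**What to change.** Reconcile Protocol 10.2, 10.2.2 and 11.8.1 with SAP 4.12.1.5. Word the follow-up-to-resolution duty in Section 10.2 in terms of the five ratings, so that *definitely related* is not left out. The natural candidate is the set that the SAP already analyses as Related. The sponsor should state explicitly whether *possibly related* is included, since that decides which duty covers most events that do not abate on stopping. Section 11.8.1 should place all five ratings and agree with the SAP. The causality criteria need no change for this purpose.

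The cost is a wording amendment, with the ethics review that protocol amendments need (Protocol 12.1 and 13.1), and contact beyond 30 days with a few subjects who have ongoing related events. No dose, treatment or stopping rule is touched.

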10.2.1 Severity of Adverse Events

All adverse events will be reported and graded, if possible, by the Common Terminology Criteria for Adverse Events (CTCAE) version 4.03 or later:

https://evs.nci.nih.gov/ftp1/CTCAE/CTCAE_4.03/CTCAE_4.03_2010-06-14 QuickReference 5x7.pdf

The severity of adverse events that cannot be graded by the most current version of CTCAE will be categorized as follows:

- Grade 1 Transient or mild discomfort; no limitation in activity; no medical intervention/therapy required
- Grade 2 Mild to moderate limitation in activity, some assistance may be needed; no or minimal medical intervention/therapy required
- Grade 3 Marked limitation in activity, some assistance usually required; medical intervention/therapy required hospitalizations possible
- Grade 4 Extreme limitation in activity, significant assistance required; significant medical intervention/therapy required hospitalization or hospice care probable
- Grade 5 Death

10.2.2 Relationship to Investigational Product

Association or relatedness to the investigational product will be graded as either "definitely related", "probably related", "possibly related", "unlikely related", or "not related". Determination of relatedness includes:

DEFINITELY RELATED – The adverse event:

- Follows a reasonable temporal sequence from administration of the study intervention
- Follows a known or expected response pattern to the suspected intervention, that is confirmed by improvement on stopping
- Reappearance of the event on repeated exposure that could not be reasonably explained by the known characteristics of the subject's clinical state

PROBABLY RELATED – The adverse event:

• Follows a reasonable temporal sequence from investigational product administration

- Abates upon discontinuation of the investigational product
- Cannot be reasonably explained by the known characteristics of the subject's clinical state.

POSSIBLY RELATED – The adverse event:

- Follows a reasonable temporal sequence from investigational product administration
- Could have been produced by the subject's clinical state or by other modes of therapy administered to the subject

UNLIKELY RELATED – The adverse event:

- Does not follow a reasonable temporal sequence from investigational product administration
- Is readily explained by the subject's clinical state or by other modes of therapy administered to the subject

NOT RELATED – The adverse event:

- Clearly not related to the investigational product and another cause of the event is most plausible
- A clinically plausible temporal sequence is inconsistent with the onset of the event
- Study intervention and/or causal relationship is considered biologically implausible

10.2.3 Adverse Event of Special Interest

As part of a formal investigation of a drug that is classified as CNS active drug within the opioid drug class, certain adverse events will be documented in more detail as part of the analysis to determine any abuse potential of nalbuphine. If a subject spontaneously reports an event, a symptom or a subjective experience that fits any of the 4 categories of AEs described below, that event should be probed with open-ended questions, such as "Can you tell me more about that?" or "Have you ever experienced that kind of feeling before?". The goal is to better understand the context and the potential clinical significance of the event or subjective experience. Importantly, this probing and additional dialogue should take place **ONLY if the subject spontaneously reports such an event or experience**. Pro-active or suggestive questioning is not recommended, since the objective is to understand what the subjects themselves identify as new and different.

Specifically, terms that relate to the following types of events should trigger the collection of additional information under the AESI section of the Adverse Event eCRF:

Categories of Special Interest:

- Experiences or events suggestive of euphoria, such as elation, exhilaration, feeling a sense of exaggerated well-being, or feeling intoxicated.
- Experiences or events suggestive of mood changes or effects, such as reports of sedation, stimulation, or impaired attention/cognition. For example, descriptions of: somnolence,

sedation, lethargy; or agitation, anxiety, restlessness; or abnormal behaviors, labile affect, and depressed mood; or poor attention, and mental or memory impairment.

- Events or descriptions that suggest dissociative or psychotic experiences, such as reports of disorientation, abnormal thoughts, hallucinations, illusions or delusions.
- Observations that suggest events of drug abuse, misuse, dependence or withdrawal. These experiences or observations may be reported by the subject spontaneously (such as reports of feeling addicted, craving investigational product, or complaints of withdrawal after stopping the investigational product). The AE may also be based on direct observations made by the Clinician and/or study staff that suggest inappropriate use of the drug, drug tampering or drug diversion. For example, repetitive or significant single-time events of missing tablets in drug accountability assessments.

The AESI section of the AE eCRF provides for recording the following details about any events meeting the characteristics described above:

- A description of the AE event in the subject's own words.
- The estimated time between the subject's most recent dose prior to the AE, and the onset time of that AE (e.g., X minutes or Y hours between preceding dose and AE onset).
- Any prior history of the same, similar or related symptoms or events, and any relevant prior diagnoses, treatments or additional details from the subject (if a subject reports dizziness, do they have a history of dizziness, vertigo or any past diagnosis of Meniere's disease?).
- Investigator comments and/or assessment.

Finally, the development of a confirmed pattern of behavior that results in a new diagnosis of drug dependency or drug abuse should be reported as an SAE.

10.3 Abnormal Laboratory Values/Vital Signs/Electrocardiograms/Physical Examinations

Laboratory abnormalities will be recorded as adverse events only if they are associated clinical symptoms/events and they worsen following the start of investigational product treatment. Clinically significant findings noted prior to the start of investigational product treatment will be recorded as medical history. The recorded adverse event will indicate the underlying abnormality or diagnosis as opposed to the observed deviation in laboratory results if the diagnosis is known.

Clinically significant worsening in physical examination, vital sign, and ECG findings following start of investigational product treatment will be recorded as adverse events. Clinically significant findings noted prior to the start of investigational product treatment will be recorded as medical history.

